### 6. Ketamine Infusions.

- a. Four Ketamine infusions will be administered over a two-week period with infusions occurring approximately on alternating days (such as Tues-Thurs) on each of two weeks; small variations to this schedule are allowed if necessitated by scheduling constraints.
- b. Patients will eat no food for 12 hours and drink no liquids for 4 hours before each infusion. Patients will be escorted by study staff to and from the Biological Studies Unit (BSU) at NYSPI, where the infusions will occur.
- c. No zolpidem or benzodiazepine will be permitted in the 24 hours prior to each ketamine infusion. We will monitor patients for signs of withdrawal, such as severe anxiety, diaphoresis, tachycardia (HR greater than 100), or hypertension (BP greater than 150/95).

- d. We exclude hypertension at screening. However, patients may be anxious at the ketamine procedure, which can transiently raise BP. We will check subjects' BP approximately 1 hour pre-ketamine, and if elevated, will have the patient do relaxation exercises. If these are ineffective, the patient will be given amlodipine 5mg po. We will allow start of the infusion with BP of 150/95 or less.
- e. Intravenous catheter will be placed by staff at the BSU or by a MIND physician or nurse, including [name].
- f. Dose: Patients will receive an intravenous infusion of saline solution with ketamine hydrochloride (0.5 mg/kg; Abbott Laboratories, North Chicago, IL) over the course of approximately 40 minutes in the BSU of NYSPI, with a study physician present at the beginning of the infusion and available throughout.
- g. Vital Signs Monitoring: During study infusion(s), blood pressure, heart rate, and oxygen saturation will be monitored as follows:
- i. -5 minutes
- ii. 0 (start of infusion)
- iii. Post start of infusion: 5, 10, 15, 20, 25, 30, 35, and 40 minutes (end of infusion)
- iv. Post end of infusion: Blood pressure will continue to be obtained until there are two measurements at least 15 minutes apart that are within 10 mmHg of the baseline diastolic blood pressure or diastolic blood pressure is below 85. Oxygen saturation will continue to be obtained until there are two measurements at least 15 minutes apart that are within normal limits (02 saturation of 94% or greater).
- h. The research assistant will remain outside the patients room during the infusion, and will record vital signs. A study physician will be available at all times. After the subject is transferred back to their inpatient unit room, the blood pressure and heart rate will be obtained manually by the unit nursing staff.
- i. Intervention for Hypertension: If the systolic blood pressure increases to ≥ 200 or diastolic blood pressure increases to ≥115 mmHg during the ketamine infusion, the infusion will be discontinued. The blood pressure will be monitored and if there is no decrease after 15 minutes, then we will initiate the following treatment interventions, consistent with our previous IRB-approved ketamine studies including IRB #6598:
- 1) One dose of sublingual nitroglycerine, 0.3 mg, will be administered.
- 2) If there is no response within 10 minutes, clonidine 0.1 mg po will be administered every 30 minutes (total maximum dose 0.6 mg clonidine) until the desired blood pressure is reached. Desired blood pressure is defined as within normal range or 10 mmHg of baseline diastolic reading.
- 3) If high blood pressure is symptomatic, i.e., blurred vision, headache, chest pain, the subject will be transferred to the ER at New York Presbyterian Hospital. If they do not respond to the above treatment (1 and 2 above) then they will be transferred to the ER.

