### 2. Side Effects of Intravenous Ketamine.

2A. Medical Risks related to Ketamine

Administration of sub-anesthetic doses of ketamine i.v., such as the 0.5 mg/kg dose to be used in this study, may induce a modest rise in blood pressure. We have administered sub-anesthetic doses of ketamine i.v. (0.5mg/kg over 40 minutes) in the setting of an IRB-approved MRI/MRS brain imaging protocol at this institution (IRB #5786, PI: [name]). The modest increases all peaked and largely resolved by 75 minutes, with vitals returning to near baseline.

In addition, ketamine may produce nausea and vomiting.

Procedures for minimizing risks related to Ketamine infusion:

Any medical risks from increased blood pressure will be minimized through the careful screening of potential subjects. Subjects will be excluded for baseline hypertension or any history of cardiovascular illness. A BLS-certified physician who has been trained in the infusion procedure will be present during the procedure. Procedures for hypertension that occurs during the infusion are described above under Study Procedures. Nausea and vomiting will be treated supportively and, if severe, with anti-emetic agents; if necessary, administration of ketamine will be discontinued. Subject will be informed that they should be fasting (12 hours no food, 4 hours no liquids) prior to the ketamine infusion.

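### Systolic pressure alone can stop the infusion, but post-infusion blood-pressure measurement and repeat treatment can both end on diastolic pressure alone

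*Combined protocol and SAP*

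**What the plan says.** All items cited by letter are in the combined protocol and SAP, Study Procedures, section 6 (Ketamine Infusions), unless stated otherwise.

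- **Stopping the infusion (item i).** The infusion is discontinued "If the systolic blood pressure increases to ≥ 200 or diastolic blood pressure increases to ≥115 mmHg during the ketamine infusion". Either component is enough. Criteria for Early Discontinuation, item d, withdraws the patient at the same two thresholds.
- **Starting drug treatment after a stop (item i).** "The blood pressure will be monitored and if there is no decrease after 15 minutes, then we will initiate the following treatment interventions". The component that must fall is not named.
- **Ending repeat treatment (item i, step 2).** Clonidine is repeated, up to a maximum total, until the target is reached: "Desired blood pressure is defined as within normal range or 10 mmHg of baseline diastolic reading".
- **Ending post-infusion measurement (item g.iv).** Pressure is taken until a pair of readings, separated by 15 minutes or more, is "within 10 mmHg of the baseline diastolic blood pressure or diastolic blood pressure is below 85".
- **After transfer (item h).** Once the patient is back on the inpatient unit, nurses take blood pressure and heart rate by hand. No frequency or action level is given.
- **Emergency-room transfer (item i, step 3).** This applies to symptomatic high pressure, and to patients who do not respond to the two drug steps.
- **Starting the infusion (item d).** "We will allow start of the infusion with BP of 150/95 or less".

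**The concern.** The rules that let a patient enter, start, stop or leave the study on blood pressure all look at both components. The two rules that close an episode do not require systolic pressure to reach any value. An episode opened by systolic pressure can therefore be closed on diastolic readings that were never abnormal.

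This is the protocol's main numeric safety rule for a risk that its own Risks section identifies, and it applies at up to four infusions per patient. If staff follow it exactly, serial measurement or repeat treatment can end while the finding that triggered it persists. If they use judgement to go further, practice will differ between patients and the written rule will not describe what was done.

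**Working it through.** There is no stated figure to reproduce. The check sets the rules side by side and then applies them to a case.

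| Rule | Place | Systolic condition | Diastolic condition |
|---|---|---|---|
| Exclusion at screening | Exclusion criterion 1 | above 140 | above 90 |
| Start of infusion | item d | at most 150 | at most 95 |
| Stop of infusion | item i | 200 or more is sufficient | 115 or more is sufficient |
| Withdrawal | Early Discontinuation, item d | 200 or more is sufficient | 115 or more is sufficient |
| End of repeat treatment | item i, step 2 | none required; the normal-range alternative may include one | no more than 10 from baseline is sufficient |
| End of serial measurement | item g.iv | none | no more than 10 from baseline, or below 85 |

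**Worked case: baseline diastolic 80, infusion stopped at 205/88.**

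1. Trigger: 205 ≥ 200 is met; 88 ≥ 115 is not. Systolic pressure alone stops the infusion.
2. Fifteen minutes later the reading is 195/88. Systolic has fallen by 205 − 195 = 10, so on that component there has been a decrease and drug treatment does not start.
3. Target: 88 − 80 = 8, and 8 ≤ 10. The diastolic alternative is met. The normal-range alternative is not needed, because the two are joined by *or*.
4. End of measurement: two readings of 195/88, 15 minutes apart, both pass the same test (8 ≤ 10).
5. At that point systolic pressure is 200 − 195 = 5 below the stopping threshold and 195 − 150 = 45 above the start limit.

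Step 2 reads the decrease on systolic pressure, the component that triggered the stop. The result does not depend on that. A patient stopped at 205/90 who falls to 195/88 shows a decrease in both components, and both diastolic values qualify (90 − 80 = 10; 88 − 80 = 8).

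**Other baselines.** With diastolic pressure 8 above baseline, the case was repeated at baseline diastolic 70, 80, 90 and 95 (readings 195/78, 195/88, 195/98 and 195/103). Both ending rules were met each time. Normal range was taken as 140/90 on both components, an assumption because the protocol does not define it. Systolic 195 fails that alternative, and the diastolic one still suffices.

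**Which baseline.** Item g.iv and item i, step 2, do not say which reading is the baseline.

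- Pre-infusion reading at the start limit: 95 + 10 = 105 qualifies.
- Screening value at the eligibility limit: 90 + 10 = 100 qualifies.

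Both exceed the diastolic start limit of 95.

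**Period covered.** The stop rule in item i and the withdrawal rule are both tied to rises during the infusion. Item g.iv requires readings afterwards, but the text does not say whether item i applies to them.

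**The case against.** The case on the other side has real content, and it limits the point in several ways.

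- **A reader might infer that the treatment target is diastolic only.** It is not. Its first alternative, normal range, names no component and can include systolic pressure. What stands is that the diastolic alternative is sufficient by itself.
- **A reader might infer that the patient is released.** Item g.iv says when serial readings may stop, not when a patient is discharged. Patients are inpatients throughout the infusion period, unit nurses take pressure after transfer, and a study physician is available. These softeners do not close the gap: the nursing checks have no stated frequency or threshold, the symptom route to the emergency room misses a patient without symptoms, and response is undefined and could be judged against the same target.
- **A reader might infer that a persistent, unchanged 205/88 goes untreated.** Item i does not support that. With no decrease after 15 minutes, drug treatment starts, and the first step does not depend on the target. The gap concerns a partial fall, as in the case above, and the point at which repeat treatment ends.
- **A reader might see a contradiction with the Risks section (2A),** which reports from another protocol that "The modest increases all peaked and largely resolved by 75 minutes, with vitals returning to near baseline". Two qualifying readings could be obtained sooner, but the statement gives no time origin and describes past experience, while item g.iv is based on a criterion. There is no contradiction.
- **A reader might say that the ending rule contradicts the start limit.** A limit for beginning an infusion and a criterion for ending serial readings serve different purposes, and 105 is only one of two possible figures. What stands is that baseline is undefined and the relation between the two limits is unstated.
- **Exposure.** A patient who reaches the stop threshold is withdrawn, so such a stop can occur at most once per patient. The 160 infusions are a ceiling on exposure, not a count of events.

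**Conclusion.** The point holds in this form: systolic pressure of 200 or more is sufficient to stop the infusion and withdraw the patient, yet serial post-infusion measurement ends on diastolic values only, and the target that ends repeat treatment can be met on diastolic values alone. Read literally, 195/88 after a stop at 205/88 with baseline diastolic 80 starts no treatment, is at target, and permits measurement to end after two such readings. Neither ending rule sets an upper limit on systolic pressure at that point.

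The conclusion rests on reading the *or* in the target as a true alternative, and on item g.iv applying after a stopped infusion as well as a completed one, which the protocol does not exclude. It does not rest on which reading is the baseline; that affects only whether 100 or 105 is the highest qualifying diastolic value. The frequency of systolic-only events is unknown. The inconsistency should be corrected, but the documents do not show that a patient would leave care with untreated hypertension.

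**What to change.** Reconcile section 6, items g.iv and i, with Criteria for Early Discontinuation, item d, so that the trigger and the ending criteria are consistent on systolic pressure. In the same revision:

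- state which reading baseline means in item g.iv and in item i, step 2, and how the allowance around it relates to the start limit in item d;
- state which component the 15-minute decrease, the normal range and the response refer to;
- state whether item i applies to readings taken after the infusion has ended.

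The study physicians decide the content and the values; none is proposed here. Blood pressure is already measured at every time point, so no new procedure is needed. The cost is a protocol wording change and somewhat longer monitoring for a few patients.

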### 7. Post-infusion Neuroimaging:

a. PET imaging with [C]UCB-J, performed identically as described above, will be repeated as close to 24-48 hours following the 4th ketamine infusion as is possible with scheduling availability of the PET Center. If participants do not complete all four ketamine infusions for any reason (including adverse effects of ketamine, lack of clinical response and preference not to complete all sessions, etc), we may conduct repeat (post-ketamine) [C]UCB-J PET scan after fewer ketamine administrations.

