# Lay Summary of Proposed Research

Lay Summary of Proposed Research

Depression is the leading cause of disability globally (1, 2). One-third to one-half of patients suffering from major depressive disorder (MDD) do not achieve remission even after multiple antidepressant trials (3). Ketamine is a commonly-used FDA-approved anesthetic medication that at subanesthetic doses leads to rapid antidepressant and anti-suicidal ideation effects in hours. rather than weeks, following administration. Despite these promising findings, a key limitation of ketamine treatment is that it only yields an antidepressant response in approximately 50% of those treated. The goal of this project is to A) elucidate ketamine's mechanism of action and B) identify biomarkers predicting treatment outcome to ketamine which could be used to match patients to treatment based on the likelihood of effectiveness at the individual level. Data from animal models suggests that ketamine acts by enhancing the connections between neurons through a process known as synaptic plasticity (4-7), and that these biological changes are responsible for the sustained behavioral effects of ketamine (8). A newly available tool allows us to image the density of these synaptic connections in the living brain using PET imaging with a radiotracer called [11C]UCB-J, which is a marker of synaptic density. We propose to directly quantify synaptic density in depressed patients before and after a course of ketamine, to examine changes in density following treatment. In exploratory analyses, we will examine synaptic density as a mediator of the sustained antidepressant effects of ketamine and as a predictor of treatment

outcome. To study these questions, we will quantify synaptic density using PET imaging before and after a course of 4 sequential intravenous infusions of ketamine administered over a two-week period.

As a further enhancement to the specific goals of this project (A: elucidate ketamine's mechanism of action; B: identify biomarkers predicting treatment outcome to ketamine), we propose to add non-invasive and cost-effective neurophysiological measures to the study protocol. Electroencephalogram (EEG) will be obtained at baseline and after ketamine treatment during two standard paradigms (at rest with eyes open/closed, loudness-dependent auditory evoked potentials [LDAEP]) that have shown 1) predictive utility for antidepressant treatment response and 2) sensitivity to ketamine administration.

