# **Background, Significance and Rationale**

Background, Significance and Rationale

Depression is the leading cause of disability globally (1, 2). One-third to one-half of patients suffering from major depressive disorder (MDD) do not achieve remission even after multiple antidepressant trials (3). Ketamine is a commonly-used FDA-approved anesthetic and non-competitive N-methyl-D-aspartate (NMDA) glutamate receptor antagonist. Recent randomized trials demonstrate that subanesthetic doses of ketamine lead to rapid antidepressant and anti-suicidal ideation effects in individuals with MDD and bipolar depression (reviewed in (9)). In contrast to current FDA-approved antidepressants, ketamine exerts antidepressant effects in hours, rather than weeks, following administration. Despite these promising findings, a key limitation of ketamine treatment is that it only yields an antidepressant response in approximately 50% of those treated. In addition, ketamine's clinical utility is limited by its acute dissociative side effects, a one to two-week duration of action as monotherapy, its addictive potential, and longterm safety concerns related to cognition and interstitial cystitis (9-11). Given the profound benefit of ketamine for some individuals yet these key limitations, developing a precision medicine research strategy for ketamine's antidepressant effects could be of tremendous scientific and clinical benefit, in order to A) elucidate ketamine's mechanism of action, to advance the development of safer alternative agents and B) identify biomarkers predicting treatment outcome to ketamine, which could be used to match patients to treatment based on the likelihood of effectiveness at the individual level.

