# **Specific Aims and Hypotheses**

Specific Aims and Hypotheses

AIM 1: Quantify changes in regional synaptic density in response to intravenous ketamine. We hypothesize that administration of ketamine in individuals with MDD will induce new spine synapse formation and synaptic protein synthesis, reflected by increased synaptic density in mPFC and HC as quantified by changes in VT derived from PET imaging with [C]UCB-J performed prior to and approximately 24 hours following a course of four ketamine infusions.

AIM 2: Evaluate the relationship between sustained improvement in depressive symptoms in response to intravenous ketamine and change in  $^{11}$ C-UCB-J binding. We hypothesize that the magnitude of the change in  $^{11}$ C-UCB-J VT in mPFC and HC in response to intravenous ketamine administration will correlate with clinical improvement on the Hamilton Depression Rating Scale from baseline to one week following the final ketamine infusion.

AIM 3: Examine whether baseline synaptic density in MDD-relevant brain regions as measured by PET imaging with [C]UCB-J predicts the magnitude of sustained antidepressant effects of intravenous ketamine treatment. Hypothesis: lower pre-treatment [C]UCB-J binding (VT) in mPFC and HC will predict greater improvement in depressive symptoms assessed one week following final ketamine infusion as assessed by the Hamilton Depression Rating Scale. This aim

is based on the assumption that individuals with MDD who have particular deficits in this biological measure (regionally-specific synaptic density) will benefit most from an intervention that acts to restore such deficits.

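### Does allowing the second PET scan after fewer than four infusions distort Aims 1 and 2?

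*Combined protocol and SAP*

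**What the plan says.** Under Specific Aims and Hypotheses, the Aim 1 scan is placed "approximately 24 hours following a course of four ketamine infusions". Aim 2 relates the VT change to Hamilton improvement "from baseline to one week following the final ketamine infusion", so the rating date moves with whichever infusion turns out to be the last.

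Study Procedures, section 6, plans four infusions over two weeks, with "infusions occurring approximately on alternating days (such as Tues-Thurs) on each of two weeks". Section 7 puts the repeat scan 24-48 hours after the fourth "ketamine infusion as is possible with scheduling availability of the PET Center". For participants who do not receive all four, whatever the reason ("including adverse effects of ketamine, lack of clinical response and preference not to complete all sessions, etc), we may conduct repeat"), the scan may follow fewer infusions. No interval from the last infusion is stated for that case.

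The Statistical Analysis Plan names linear mixed effects models for the primary aims, two-sided tests at 0.05 and model diagnostics, and calls the study a pilot. It defines no analysis set and does not mention incomplete courses.

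**The concern.** Two things look wrong. First, the aim describes one exposure and the procedures allow several. The Background says of ketamine that "it only yields an antidepressant response in approximately 50% of those treated", so non-response will be common, and it is a named reason for stopping. Someone who stops for non-response has both fewer infusions and less improvement. If VT change grows with the number of infusions, pooling such scans with full-course scans would produce part of the correlation that Aim 2 hopes to find, and would pull the Aim 1 estimate down.

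Second, timing cannot be repaired at analysis. On the Tuesday-Thursday example the infusions fall on days 1, 3, 8 and 10 and the scan on day 11-12. If a participant stopped after infusion 1 or 2 and kept the booked slot, the scan would come 10-11 or 8-9 days after the last infusion. The Aim 2 rating would fall on day 8 or 10, which is 1-4 days before the scan. The Background describes "a one to two-week duration of action as monotherapy", and the Lay Summary reports animal data suggesting that "these biological changes are responsible for the sustained behavioral effects of ketamine", so a late scan might miss a fading effect.

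**Working it through.** The documents give no power, effect size, SD of VT change or rate of incomplete courses, so there is no stated figure to reproduce. The check asks how large the distortion would be over a range of assumptions.

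**Inputs**
- n = 20 scanned. The completer field prints 2.0 against 40 enrolled; 20 is an assumption.
- Half respond (Background).
- SD of VT change = 4.5 × √(π/2) = 5.6 percentage points, reading the Background's 4-5% test-retest variability as a mean absolute difference.
- Assumed: a share s = 10, 25 or 50% of non-responders stop after k = 1, 2 or 3 infusions with equal chance, are rescanned promptly and are pooled. Early stoppers are then p = s/2 of all scanned (1, 2.5 or 5 of 20).
- Assumed: four-infusion VT change D = 5, 10 or 15%, with no true link between VT change and improvement.
- Share of effect present after k infusions: linear k/4 (mean over k = 1-3: 0.50), or diminishing (1 − 0.5^k)/(1 − 0.5^4) = 0.533, 0.800, 0.933 (mean 0.756).

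**Aim 1.** Expected estimate = D × [1 − p(1 − mean share)]. For D = 10:

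| s | linear | diminishing |
|---|---|---|
| 10% | 10 × (1 − 0.05 × 0.50) = 9.8 | 10 × (1 − 0.05 × 0.244) = 9.9 |
| 25% | 10 × (1 − 0.125 × 0.50) = 9.4 | 10 × (1 − 0.125 × 0.244) = 9.7 |
| 50% | 10 × (1 − 0.25 × 0.50) = 8.8 | 10 × (1 − 0.25 × 0.244) = 9.4 |

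The standard error is 5.6/√20 = 1.25 points, so the shift is about one standard error at most.

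**Aim 2.** With standardised improvement, the lower half averages −0.798. The induced covariance is 0.798 × p × D × (1 − mean share). Divide by the SD of VT change, √(5.6² + D² × variance of the share), to get r. With z = atanh(r) × √17, type I error ≈ Φ(−1.96 + z) + Φ(−1.96 − z).

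- Middle case, linear (s = 25%, D = 10): covariance 0.798 × 0.125 × 5 = 0.499; SD √(31.36 + 3.26) = 5.88; r = 0.085; z = 0.35; type I error 6.4%.
- Middle case, diminishing: covariance 0.798 × 0.125 × 2.44 = 0.244; SD 5.69; r = 0.043; z = 0.18; type I error 5.4%.
- Extreme case, linear (s = 50%, D = 15): covariance 0.798 × 0.25 × 7.5 = 1.496; SD √(31.36 + 12.89) = 6.65; r = 0.225; z = 0.94; type I error 15.7%.

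Simulation with a Pearson test gives 6.4%, 5.4% and 15.8% for the same cases. An observed r needs to reach 0.44 for significance at n = 20, so an induced 0.04-0.09 does little. At 10% stopping the simulated error is 4.8-5.4% over both curves, and 0.9^10 = 35% of trials would contain no early stopper. If the effect is complete after one infusion and the scan is prompt, the error stays at about 5%. If half of the stoppers stop for reasons unrelated to response, the middle case is 5.2-5.9% over all curves tested, including late-scan ones.

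**Would another analysis set be better?** At a true r of 0.5 with no dose effect, the all-scanned analysis gives mean r 0.49 and power 0.64.

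| s | four-infusion-only: kept / mean r / power | adjusted for infusions: mean r / power |
|---|---|---|
| 10% | 19 / 0.49 / 0.62 | 0.49 / 0.62 |
| 25% | 17.5 / 0.49 / 0.58 | 0.48 / 0.60 |
| 50% | 15 / 0.47 / 0.47 | 0.46 / 0.55 |

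Restricting to four infusions also selects responders, and estimates a true 10% Aim 1 change at 10.1, 10.3 and 10.7%. Both alternatives condition on something that may be a consequence of response.

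**The case for a change.** The strongest case for a change is that no document fixes the stopping rate, so a small bias cannot be assumed. If 20 completers come from 40 enrolled, the plan tolerates 50% loss. With early scans at 25-50% of all scans, a separate set of assumptions gives Aim 2 type I error up to 15-20% and keeps as little as 50-75% of the Aim 1 effect. If the booked slot is kept and the VT effect fades to zero over 7 days, the error reaches 25% at the extreme. Pooling and restriction move Aim 1 in opposite directions, so choosing after seeing the data is a real freedom.

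Part of this stands. The size cannot be settled from the documents, and Aim 1 is not immune. With a 5% change and an added 5% patient-to-patient SD, the standard error is √(5.6² + 5²)/√20 = 1.68. Power is then 0.81 with no loss of effect, and 0.59-0.76 at 50% stopping for every curve except completion after one infusion.

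The larger figures are weaker than they look. The 50-75% retention assumes no infusion at all, whereas section 7 describes a post-ketamine scan. The 50% enrolment allowance covers loss at every stage. The fade borrows the antidepressant duration for VT, and applies it to non-responders who have little such effect to lose. The late scan also runs against the protocol: section 4 aims for the shortest possible admission, and section 8 and Research Related Delay to Treatment start open treatment once the second scan is done. Those passages fix no interval, but they make a prompt scan the natural reading. Criteria for Early Discontinuation withdraws some early stoppers from the study altogether, which may reduce the number of such scans; it has to be read together with section 7, which does not mention it.

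**Conclusion.** The observation is accurate, but no change to the plan follows. The protocol accepts an early scan rather than lose the participant's second measurement, which is a fair trade-off in a pilot. The analysis set is a detail that an analyst fills sensibly: infusion and scan dates show who had a short course and when the scan took place, and those few participants can be described individually. Requiring a four-infusion-only or infusion-adjusted analysis would exchange one modest bias for another and lose power. A stated interval would matter only if early scans were in practice left to the booked slot, which nothing in the documents indicates.

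On the central assumptions, Aim 2 type I error is 5.4-6.4% and Aim 1 is diluted from 10% to 9.4-9.7%. With about one early stopper both effects are negligible. The conclusion rests on 20 scanned participants, prompt scans, and early stoppers making up about an eighth of those scanned. It also rests on a Pearson test standing in for the mixed model. If completers means participants with all four infusions, early scans come on top of the 20 and the loss from restricting is smaller. If a quarter of those scanned were non-responders who stopped early and VT rose in proportion to infusions, Aim 2 error could reach about 16%, and the published correlation should then be read with that in mind.
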